We designed the present randomized trial to test whether 12 weeks of supervised weekly Kundalini yoga class and a brief daily home meditation practice can improve cognitive function among older women with high AD risk compared to weekly classes of memory training with daily homework. Our choice of interventions is based on prior studies of mind-body exercise in older adults that revealed robust cognitive benefit, as well as our own studies of this intervention compared to cognitive memory training in older adults with MCI. Kundalini yoga has also been observed to impact the frontal lobes, likely due to increased cerebral blood flow ([name] et al., 2013b).

The primary outcome will be memory performance at 12 weeks (i.e., immediately post-treatment).

Secondary outcomes include measures of executive functioning and changes in brain structure and connectivity.

Specific Aim 1: To evaluate effects of Kundalini Yoga+ Kirtan Kriya (KK+KY) and Memory Enhancement Training (MET) on memory performance in women with high AD risk.

Hypothesis 1: Improved memory performance will be observed in women receiving KK+KY and MET at 12 weeks compared to baseline.

Specific Aim 2: To test the efficacy of KK+KY vs. MET for improving executive functioning including working memory.

Hypothesis 2: KK+KY will improve performance in executive functioning to a greater extent than MET.

Exploratory Aim 3a: To test the effects of MET vs. KK+KY on structural and functional connectivity and task-related activation for working and episodic memory.

Hypothesis 3a: Compared to MET, KK+KY will be associated with greater improvement in connectivity in regions associated with working and episodic memory.

Exploratory Aim 3b: To test the effects of MET vs. KK+KY on levels of cellular and genomic markers of inflammation, telomerase activity level, and telomere length after 12 weeks and at 6 and 12 month follow-up.

Hypothesis 3b: Compared to MET, KK+KY will be associated with decreases in cellular and genomic markers of inflammation and increases in telomerase activity level and telomere length after 12 weeks and at 6 and 12 month follow-up.

Exploratory Aim 3c: To explore whether KK+KY results in reduced cardiovascular risk factors compared to MET, and whether this effect will correlate temporally with changes in fMRI measures and clinical outcomes.

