Data will be analyzed using the SAS (v9.4) statistical package. Data will be examined initially to identify issues such as departures from normality, which might suggest the need for transformation (e.g., logarithmic). Demographic variables (e.g., age, gender, etc.) will be compared by treatment group and examined in relation to outcome variables; this would define one possible set of appropriate covariates, if needed. Correlations (a) among outcome measures and (b) among potential covariates will be examined to eliminate redundancy via possible data reduction, e.g., formation of composite scores or selection of single measures from sets of highly inter-correlated variables. Cognitive domain scores will be obtained as follows: for each neuropsychological test, raw scores will be converted to standardized (Z) scores with a mean of 0 and a SD of 1, based on all participants combined. Then, for each of the tests in a cognitive domain, the Z scores will be averaged to create a single Z score per cognitive domain.

The independent samples *t*-test or Chi-square test will be used to compare the demographic characteristics between the MET and KK+KY control group. The effect of intervention over time on the cognitive functions will be investigated in intention-to-treat (ITT) analyses. Measurements will be analyzed using linear mixed models; analyses will assume missing at random with missingness allowed. All models will include random intercepts to account for correlations between the repeated measures for each participant. The fixed components of the models will include effects of group and time and a group X time interaction, with post hoc analyses between times and groups. All statistical significance tests will be two-sided, and an alpha-level of 0.05 will be considered statistically significant for primary analyses and Bonferroni correction will be employed for post hoc analyses.

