Primary outcome: The analyses for the memory domain Z scores will use general linear mixed model (GLMM) analysis (e.g., SAS PROC MIXED). The two treatment groups will be compared for time course of cognitive domain z scores the initial endpoint EOT at 12 weeks and 6- and 12-months. Covariates may be included in the model as noted above. As noted above, the primary cognitive domain of interest for this proposal is memory. A separate GLMM as above will be estimated using memory domain z-scores as dependent variables. Executive Function will be examined as secondary outcome measure. Supplementary analyses of the follow-up period will look at the cognitive domain scores by treatment group controlling for values at EOT (post-treatment changes). Objective memory measures will be examined using a similar GLMM.

Exploratory Hypotheses: GLMM models as described above will be used to examine telomerase activity (overall level and TL) and inflammatory measures separately. Relationships between changes in markers of inflammation and telomerase activity to changes in cognitive scores, cognitive domain scores and fMRI measures will be examined using regression models within each group. Transformations of the measures will be performed as necessary.

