Power analysis: The power analysis is focused on the primary aim of the study to assess whether the KK+KY and MET groups demonstrate comparable improvement in memory performance. We plan to enroll a total of 100 women in the study, anticipating an attrition rate of at most 10% based on our previous studies. Thus, we will most likely have a total of 90 completers. With a sample size of 45 per group, we achieve 80% power to detect equivalence within a margin of equivalence of 0.62, when the true difference between the means is assumed to be zero. In the PI's previous study using similar interventions on older adults with MCI, a between-group effect size of 0.3-0.4 was observed for the memory measures. In the proposed study, the target population is women with high risk for AD, hence we believe that the proposed sample size will have sufficient power to address the primary hypothesis of the study. With this sample size, we can also expect to detect an effect size of 0.60 at a significance level of 0.05 and 80% power for the secondary outcome measure (executive functioning). We intend to test the secondary outcomes adjusting for multiple comparisons using the Benjamini-Hochberg false discovery rate approach (which is more powerful than the simple Bonferroni correction). Further, we will report results of all proposed analyses and conclusions will be based on the pattern of results.

Data management: Data management and analysis support will be provided by the UCLA Semel Institute Statistical Core (SI-Stat) ([name]). The SI-Stat will provide needed software and technical support with a data manager operating under the supervision of [name]. The SI-Stat has a Dell PC computer network with

automated CD R/W backup and is set up for medium to large-scale data processing and analysis using available commercial database and statistical software. **1. Randomization.** Randomization schedules will be prepared in a masked manner by the statistician. **2. Data submission and quality control.** Data forms will be delivered from the originating location to the central data unit within one week of being generated. When errors, omissions, or unclear information is detected on the paper forms, a copy will be returned for corrections. The data manager will generate monthly reports summarizing missing and incorrect data will be sent to the PI.

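### The primary endpoint is memory at week 12, but no week-12 between-arm test is named as primary, and the 80% power is for an equivalence test that the analysis section does not contain

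*Combined protocol and SAP*

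**What the plan says.** **Endpoint.** In the Specific Aims, the primary outcome "will be memory performance at 12 weeks (i.e., immediately post-treatment". Hypothesis 1, just below, concerns change within each arm: "Improved memory performance will be observed in women receiving KK+KY and MET at 12 weeks compared to baseline".

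**Model.** The Data analysis section specifies a linear mixed model with group, time and "a group X time interaction, with post hoc analyses between times and groups". On error rates it says "an alpha-level of 0.05 will be considered statistically significant for primary analyses and Bonferroni correction will be employed for post hoc analyses". It does not define the primary analyses and does not count the post hoc ones.

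**Memory analysis.** The Primary outcome paragraph says "The two treatment groups will be compared for time course of cognitive domain z scores" and lists end of treatment at 12 weeks together with 6 and 12 months. It does not rank the visits.

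**Power.** The Power analysis paragraph gives the primary aim as "to assess whether the KK+KY and MET groups demonstrate comparable improvement in memory performance". It claims 80% power for equivalence within 0.62 with 45 per group and a true difference of zero. It ends by saying that "conclusions will be based on the pattern of results".

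**Schedule.** Measures and Outcomes says in one place that all outcome measures are given at baseline, week 12, 6 and 12 months. The sentence introducing the neuropsychological tests, and Table 4, give that battery at baseline and the two later follow-ups only.

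**The concern.** A single-time endpoint needs a test of that time. Here the arms are compared over the whole course, and the comparison of arms at one visit reads as a post hoc contrast. A time-course test can be significant because of the 6- or 12-month visits alone, and a real week-12 result may have to pass a stricter, unspecified threshold.

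The power statement does not settle which test is meant. It is for equivalence, yet the analysis section contains no margin, confidence interval or equivalence test. A non-significant group difference or interaction could then be reported as comparable improvement, which it does not show. At stake is the rule by which the trial's main conclusion on memory is reached.

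**Working it through.** **Inputs.** From the Power analysis: n = 45 completers per arm, margin 0.62, true difference 0, power 80%. From Data analysis: 0.05 for primary analyses, Bonferroni for post hoc. Assumed: the margin is in SD units (no unit is given). The family size k is also assumed, since none is stated.

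**1. Reproducing the stated power.** Two one-sided tests (TOST) at level α each, SD 1, true difference 0:

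power = 2Φ(0.62/√(2/n) − z₁₋α) − 1.

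- √(2/45) = 0.2108, and 0.62/0.2108 = 2.941.
- With α = 0.05: 2.941 − 1.645 = 1.296, Φ = 0.9025, power = **80.5%** (79.8% by simulation with the t distribution).
- Required n = 2[(1.645 + 1.282)/0.62]² = 44.6, so 45 per arm.
- With α = 0.025 per one-sided test the result is 67.3%, and 55 per arm would be needed.

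The plan's figure is therefore one between-arm comparison with no multiplicity correction, equivalent to a 90% confidence interval lying within ±0.62.

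**2. The same comparison under Bonferroni, α = 0.05/k.**

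| k | z₁₋α | 2.941 − z | Power | n per arm for 80% |
|---|---|---|---|---|
| 1 | 1.645 | 1.296 | 80.5% | 45 |
| 2 | 1.960 | 0.981 | 67.3% | 55 |
| 3 | 2.128 | 0.813 | 58.4% | 61 |
| 4 | 2.241 | 0.700 | 51.6% | 65 |
| 6 | 2.394 | 0.547 | 41.6% | 71 |

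The case k = 3 is one arm contrast at each of week 12, 6 and 12 months.

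**3. What the mixed model could recover.** For the contrast in change from baseline with visit correlation r, the standard error is √(2(1 − r) × 2/n).

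- At r = 0.5 this equals 0.2108, so the table is unchanged.
- At r = 0.7 it is 0.1633, and 0.62/0.1633 = 3.797. At k = 3: 3.797 − 2.128 = 1.669, Φ = 0.952, power about 90%.

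The documents give no r.

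**4. Does a time-course test speak to week 12?** Take the 3-df interaction over four visits with equal variances, constant correlation r and complete data. For arm differences dⱼ the noncentrality is λ = n/[2(1 − r)] × Σ(dⱼ − d̄)², referred to F(3, 264). At r = 0.5 the multiplier is 45.

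- Differences 0, 0, 0.6, 0.6 SD (none at week 12): λ = 45 × 0.36 = 16.2, rejection 93%.
- Differences 0, 0, 0, 0.6 SD: λ = 45 × 0.27 = 12.15, rejection 84%.

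A higher r raises both. A significant time-course result can therefore go with a week-12 difference of exactly zero.

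**The case against.** The strongest reply is that the plan can be read sensibly. The Specific Aims name week 12, the Primary outcome paragraph calls it the initial endpoint, and follow-up analyses adjusting for end-of-treatment values are labelled supplementary. On that reading the week-12 memory comparison is the primary analysis at 0.05, and Bonferroni applies only to the remaining pairs. This is possible, but the text does not say it. All three visits stand together under Primary outcome, and comparisons between groups and times are called post hoc without exception.

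Some stronger readings are tempting, and the documents do not support them:

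- **That the interaction is the test run at 0.05.** The Data analysis section lists it as a model term and ties 0.05 only to undefined primary analyses.
- **That the 0.60 effect size describes power for memory.** That figure, with its explicit 0.05 and 80%, belongs to executive functioning, whose multiplicity is handled by Benjamini-Hochberg.
- **That the closing remark on the pattern of results permits a null week-12 finding to be replaced by another signal.** It follows the sentence on secondary outcomes and is joined to a promise to report every analysis. It is loose, but it does not say that.
- **That the interaction is weak for a real week-12 effect.** For a 0.6 SD effect fading by about half or more, its power is 65–70% at r = 0.5 but 88–91% at r = 0.7.

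**Conclusion.** The point stands as a mismatch between endpoint, test and power statement. The endpoint is week-12 memory, but no week-12 between-arm contrast is named as the primary test. As written, that contrast reads as one of an uncounted Bonferroni family. The 80% for memory holds for a single uncorrected equivalence comparison within 0.62 (80.5%), which the analysis section does not include. In the two-group calculation, correction would take it to 67% for 2 contrasts and 58% for 3.

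Those two figures rest on an assumed family size, a margin in SD units, 45 completers per arm and no gain from repeated measures. A reader might infer that the trial is underpowered. That does not follow, because with r = 0.7 the model contrast keeps about 90% even at k = 3. The conclusion is that the stated power does not describe the planned test, and that the rule for the main memory conclusion is left open.

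**What to change.** Amend the Data analysis section, before the data are analysed, to say:

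1. The one primary test is the 1-df KK+KY minus MET contrast in the memory domain score at week 12, estimated from the mixed model. It stands outside the post hoc Bonferroni family.
2. To match the Power analysis, comparability is concluded if the 90% confidence interval for that contrast lies within ±0.62. State the unit of the margin: an average of several correlated z-scores generally has an SD below 1, so SD units and domain-score units differ. State also that these paired one-sided tests are an exception to the two-sided rule. A 95% interval would give 67.3% in the same calculation.
3. A non-significant difference or interaction is not evidence of comparability.
4. The 6- and 12-month contrasts are secondary. The within-arm changes of Hypothesis 1 are supportive. Give the number of contrasts that share the Bonferroni correction.
5. The memory conclusion rests on the week-12 contrast, and other results are supportive. This replaces the remark on the pattern of results as far as memory is concerned.

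The two statements in Measures and Outcomes and Table 4 must also be reconciled on whether the neuropsychological battery is given at week 12. Without those scores the contrast cannot be estimated.

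The analysis changes cost a few sentences, with the same model and sample size. If the battery is not in fact scheduled at week 12, the cost is greater, because the endpoint and the schedule must then be brought into agreement.

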Kirtan Kriya (KK). Participants will be asked to engage in 12 minutes of daily KK meditation. Meditations will be guided by standardized CDs distributed to participants that can be practiced at home. The protocol for KK is a standard ancient chanting meditation for the Kundalini Yoga practice as taught by Yogi Bhajan and as utilized in previous studies in older adults (Andrew B. Newberg, Wintering, Khalsa, Roggenkamp, & Waldmanb, 2012). The meditation involves repetitive finger movements or mudras, as well as chanting of the mantra "Saa, Taa, Naa, Maa," meaning "Birth, Life, Death, and Rebirth" first chanted aloud, then in a whisper, and silently for the total of 11 minutes with 1 minute allocated to "tuning in" at the beginning and the final deep breathing relaxation accompanied by the visualization of light.

Alternate treatments. All participants will be medically stable prior to entry into the study protocol. However, if participants engage in alternate treatments, they will be advised to inform the PI. Upon completion of the research procedures, yoga classes will be offered to participants who participated in MET and vice versa.

Treatment expectancy/ credibility. Our study has been designed to promote equal perception of treatment expectancy/ credibility between groups. We will evaluate treatment credibility, expectation for change, and satisfaction after the 2nd session of treatment and at post-intervention using a 10-point Likert scale, as we have done in our pilot study.

Dosing effects. We will distribute and collect home practice logs to determine the relationship between practice and outcomes. The extent to which participants continue to practice skills learned during the intervention period will also be assessed at 6-month and 12-month follow up. As in previous studies, we will also ask participants in both intervention groups to keep a brief weekly journal about any changes they have noticed that they attribute to the intervention. This data will be analyze through qualitative analysis at the completion of the study. **Data analysis.** Primary analyses will be carried out on an intent-to-treat basis; additional analyses considering dropout or other observable post-randomization outcomes will make use of an instrumental-variable analysis framework.

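### The supplementary follow-up analysis conditions on the week-12 score, so its group term does not measure the post-treatment change it is labelled as

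*Combined protocol and SAP*

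**What the plan says.** The Primary outcome paragraph of the Data analysis section describes two looks at the follow-up period.

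- **Main comparison.** "The two treatment groups will be compared for time course of cognitive domain z scores the initial endpoint EOT at 12 weeks and 6- and" 12 months. The model is set out just before: "The fixed components of the models will include effects of group and time and a group X time interaction", and "All models will include random intercepts to account for correlations between the repeated measures for each participant". Post hoc comparisons between times and groups are planned. No EOT covariate is stated.
- **Supplementary comparison.** "Supplementary analyses of the follow-up period will look at the cognitive domain scores by treatment group controlling for values at EOT (post-treatment changes". The parenthesis shows that the intended quantity is change after treatment ends.

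The plan does not say how the group term of the supplementary model will be interpreted. At the start of Data analysis it says that "additional analyses considering dropout or other observable post-randomization outcomes will make use of an instrumental-variable analysis framework", but not whether the EOT-adjusted analysis falls under that framework. The Power analysis paragraph says that every proposed analysis will be reported and that conclusions will follow the pattern of results.

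**The concern.** Randomisation makes the arms comparable at baseline. It does not make them comparable at week 12, where a treatment effect may already have separated them. Take two women with the same week-12 score, one from each arm. The woman in the lower-scoring arm stands further above her own arm's mean, so she is expected to fall back more by the next visit. A model that conditions on the week-12 score sees this as a group difference at follow-up, even if nothing changed after classes ended.

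At stake is the reading of durability. Long-term benefit is a stated purpose of the trial (Abstract; Study Design; Study intervention procedures), and this is the only analysis labelled as post-treatment change. If its group term is taken at face value, the arm that was better at 12 weeks could be described as still gaining when it has only held its ground. An effect that has partly faded could be described as maintained.

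**Working it through.** **Inputs from the documents**
- Two-sided testing at 0.05 is stated for primary analyses: "All statistical significance tests will be two-sided, and an alpha-level of 0.05 will be considered statistically significant for primary analyses". The same threshold is used here.
- Completers at 12 months: 35–36 per group (Recruitment). The upper figure is 50 × (1 − 0.10 − 0.10 − 0.08) rounded from successive losses, or simply 50 × 0.9 × 0.8 = 36.
- Effect sizes: for memory in the earlier MCI study, "a between-group effect size of 0.3-0.4 was observed for the memory measures". For executive function, 0.60 is given as the detectable effect. It is not given as an expected effect.

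**Assumptions.** Equal SDs at EOT and follow-up, d in SD units of the domain score, and ρ of 0.6–0.8. The documents give no correlation between visits.

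**Step 1: the plan's own figures.** No stated figure concerns the EOT-adjusted analysis. Those in the Power analysis paragraph reproduce.
- "With a sample size of 45 per group, we achieve 80% power to detect equivalence within a margin of equivalence of 0.62": with SE = √(2/45) = 0.211 and two one-sided 0.05 tests, power = 2Φ(0.62/0.211 − 1.645) − 1 = 80.5%.
- Effect size 0.60, two-sided 0.05: Φ(0.60/0.211 − 1.96) = 81.2% (80.4% by noncentral t).

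**Step 2: what the adjusted term estimates.** The within-arm slope of the follow-up score on the EOT score is ρ when the SDs are equal. So

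group coefficient = d_followup − ρ·d_EOT.

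- Effect fully maintained (both equal d): d(1−ρ).
- Effect faded to ρd: 0.
- Arms equal at both times: 0.

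**Step 3: size with 36 per arm, effect fully maintained.** SE = √(1−ρ²)·√(2/36), and P = 1 − Φ(1.96 − b/SE) + Φ(−1.96 − b/SE), where b = d(1−ρ). Each cell gives the bias in SD and the chance of p < 0.05.

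| d | ρ = 0.6 (SE 0.189) | ρ = 0.7 (SE 0.168) | ρ = 0.8 (SE 0.141) |
|---|---|---|---|
| 0.3 | 0.12, 10% | 0.09, 8% | 0.06, 7% |
| 0.4 | 0.16, 14% | 0.12, 11% | 0.08, 9% |
| 0.6 | 0.24, 25% | 0.18, 19% | 0.12, 14% |

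For d = 0.4 and ρ = 0.7: b = 0.4 × 0.3 = 0.12, SE = 0.714 × 0.236 = 0.168, b/SE = 0.713, P = 11%.

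**Step 4: sensitivity.** With 35 per arm, ρ from 0.5 to 0.9 and the SE enlarged for the arm difference in the covariate, the same three effects give 6%–28%.

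**Step 5: simulation** (8,000 trials per scenario, random-intercept data, 35 per arm, ρ = 0.7).

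| Scenario | EOT-adjusted term, rejection | Follow-up minus EOT contrast, rejection |
|---|---|---|
| d = 0 | 0.00, 5% | 0.00, 5% |
| d = 0.4 maintained | 0.12, 10% | 0.00, 5% |
| d = 0.6 maintained | 0.18, 17% | 0.00, 5% |
| d = 0.4 faded to 0.28 | 0.00, 5% | −0.12, 9% |
| d = 0.6 faded to 0.42 | 0.00, 5% | −0.18, 16% |

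The simple contrast gives the true change in each case. Adding the baseline score to the EOT-adjusted model does not repair it. With d = 0.6 maintained, the slope on EOT falls to ρ/(1+ρ) = 0.7/1.7 = 0.412, so the term rises to 0.6 × (1 − 0.412) = 0.35. The simulation gave 0.35 with 52% rejection.

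**Step 6: cost of the contrast.** Its SE relative to the adjusted model is √(2(1−ρ))/√(1−ρ²). At ρ = 0.7 this is 0.775/0.714 = 1.085.

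**The case against.** The strongest reply is that this is a supplementary analysis beside a sound main one. The mixed model compares the arms at 12 weeks, 6 months and 12 months with a group × time term, and it already contains the unbiased contrast. That stands. A reader might infer that the follow-up comparisons as a whole adjust for EOT, or that this is the trial's analysis of durability. The documents do not support either, because the EOT covariate appears only in the supplementary sentence.

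A second reply is that the distortion needs a real difference at EOT. For memory, the power analysis assumes a true difference of zero, and then there is no bias. This also stands, but it does not clear the analysis. The sentence covers cognitive domain scores generally, and Hypothesis 2 predicts that KK+KY will beat MET on executive function. Nor were the arms equal on memory in the earlier study. In Table 2 the week-12 gaps favour MET by 21.22 − 18.90 = 2.32 on Rey-O 3-min (pooled SD 6.81, or 0.34 SD) and by 28.90 − 27.14 = 1.76 on HVLT total (pooled SD 5.62, or 0.31 SD). These are raw gaps and include small baseline differences.

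A third reply is that whether women with equal EOT scores later differ by arm is a legitimate conditional question. It is, but its answer is not post-treatment change, and that is the label the plan gives it.

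**Conclusion.** The supplementary model does not estimate the quantity its label names. When an EOT difference d is maintained, its group term is d(1−ρ), with the sign of the week-12 effect. Under equal SDs, 36 per arm, d of 0.3–0.6 and an assumed ρ of 0.6–0.8, the bias is 0.06–0.24 SD and the false-positive rate about 7%–25%. The upper end pairs the detectable executive-function effect with the lowest ρ in that range.

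A reader might infer that the trial would report continued gain. The figures do not support that. At d = 0.4 and ρ = 0.7 about 89% of trials with a maintained effect would show no significant adjusted difference. This is a risk of misreading, in both directions. It does not reach the primary comparison. It still merits correction, because the plan commits to reporting all analyses and drawing conclusions from their pattern, and gives no rule for reading this one.

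**What to change.** Define post-treatment change as the between-arm contrast of month 6 minus week 12, and of month 12 minus week 12, from the group × time mixed model already specified. Then either delete the adjustment for EOT, or keep that result as a descriptive analysis conditional on the week-12 score and not labelled as change. No extra baseline adjustment is needed for the contrast, since a baseline main effect cancels from it.

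The programming cost is one contrast statement per follow-up visit. The statistical cost is a standard error about 8–9% larger at ρ = 0.7 (12% at ρ = 0.6, 5% at ρ = 0.8).

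Both versions need week-12 cognitive scores. The Neuropsychological tests paragraph and the assessment schedule (Table 4) place the battery at baseline and at the 6- and 12-month visits, with none at week 12. The opening of Measures and Outcomes has every outcome measured at week 12 as well. These passages must be reconciled before either analysis can be specified.
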